ACASI	Audio Computer Assisted Survey Instrument
AE	adverse event
ALT	alanine aminotransferase
AST	aspartate aminotransferase
BUN	blood urea nitrogen
CBC	Complete blood count
CBO	Community based organization
CCG	Community Consulting Group
CFR	Code of Federal Regulations
CRF	case report form
CPHR	Center for public health research
DMC	Data Monitoring Committee
DSMB	Data Safety Monitoring Board
DSM-IV	Diagnostic and Statistical Manual for Mental disorders
EtG	ethylglucuronide test
FDA	Food and Drug Administration
GCP	Good Clinical Practice
GEE	generalized estimating equations
HIPAA	Health Insurance Portability and Accountability Act of 1996
HIV	Human Immunodeficiency Virus
ICF	informed consent form
ICH	International Conference on Harmonisation
IEC	Independent Ethics Committee
IRB	Institutional Review Board
MM	Medical Management counseling
MSM	Men who have sex with men
NIAAA	National Institute on Alcohol Abuse and Alcoholism
PEth	phosphatidylethanol
PrEP	pre-exposure prophylaxis
PI	Principal Investigator
SAE	serious adverse experience
SAMHSA	Substance Abuse and Mental Health Services Administration
SCID	Structural clinical interview for DSM disorders
SFDPH	San Francisco Department of Public Health
SMS	Text message
TLFB	Timeline follow-back

PROTOCOL SYNOPSIS

TITLE	The Better THAN Study: Targeting Heavy Alcohol use with Naltrexone among MSM
SPONSOR	[name]
FUNDING ORGANIZATION	National Institute on Alcohol Abuse and Alcoholism (NIAAA)
NUMBER OF SITES	1 site
RATIONALE	Oral naltrexone, FDA approved agent, was chosen because we believe it will be more acceptable to non-treatment seeking, non-alcohol dependent binge drinking men who have sex with men (MSM). Intermittent dosing makes sense for most binge-drinking MSM because data indicate that they do not binge drink daily.
STUDY DESIGN	This is a randomized, double-blind, placebo-controlled phase 2 study.
PRIMARY OBJECTIVE	To determine the efficacy of targeted naltrexone versus placebo in reducing binge drinking among non-dependent MSM, as determined by number of binge drinking days in timeline follow-back (TLFB), over the three-month treatment period.
SECONDARY OBJECTIVES	To determine the efficacy of targeted naltrexone versus placebo in reducing alcohol consumption among non-dependent MSM, as determined by the proportion of ethyl glucuronide (EtG) positive urines, over the three-month treatment period.
NUMBER OF SUBJECTS	120
SUBJECT SELECTION CRITERIA	
Inclusion Criteria: (1) Male gender (2) self-reported anal sex with men in the prior three months while under the influence of alcohol (3) at least one binge drinking (five or more drinks on a single occasion) session per week in the prior three months; (4) interested in reducing binge alcohol consumption; (5) HIV-negative by rapid antibody test or medical record documentation of HIV infection (HIV positive participants); (6) no current acute illnesses requiring prolonged medical care; (7) no chronic illnesses that are likely to progress clinically during trial participation; (8) able and willing to provide informed consent and adhere to visit schedule; (9) age 18-70 years; (10) baseline CBC, total protein, albumin, glucose, alkaline phosphatase, creatinine, BUN, and electrolytes without clinically significant abnormalities as determined by study clinician in conjunction with symptoms, physical exam, and medical history.
 
Exclusion Criteria: (1) Any psychiatric (e.g. depression with suicidal ideation) or medical condition that would preclude safe participation in the study; (2) known allergy/previous adverse reaction to naltrexone; (3) current use of/ dependence on any opioids or a known medical condition which currently requires/may likely require opioid analgesics; (4) opioid-positive urine at enrollment; (5) current CD4 count < 200 cells/mm³ (6) moderate/severe liver disease (AST, ALT \geq 3 times upper limit of normal);

	(7) impaired renal function (creatinine clearance < 50 ml/min); (8) currently participating in another intervention research study with potential overlap; (9) alcohol dependence as determined by SCID criteria (participants with non-dependent alcohol use disorders/symptoms of alcohol abuse [per DSM-IV] are eligible) (10) any condition that, in the principal investigator and/or study clinician's judgment interferes with safe study participation or adherence to study procedures; (11) not having a cell-phone that can send and receive text messages.
TEST PRODUCT, DOSE, AND ROUTE OF ADMINISTRATION	Naltrexone HCL 50 mg (ReVia), oral administration as needed.
CONTROL PRODUCT, DOSE AND ROUTE OF ADMINISTRATION	Placebo 50 mg, oral administration as needed.
DURATION OF SUBJECT PARTICIPATION AND DURATION OF STUDY	Subjects will be on study for up to 9 months Screening: up to 30 days Treatment: 3 months Follow-up: 6 months The total duration of the study is expected to be nine months. One month for subject recruitment and nine months for final subject participation and follow-up.
CONCOMITANT MEDICATIONS	Allowed: standard therapy Prohibited: current use of/ dependence on any opioid medication or current naltrexone treatments.
EFFICACY EVALUATIONS	
PRIMARY ENDPOINT	
 • To detect 27% reductions in numbers of binge drinking occasions, as well as 10% reductions in the average numbers of drinks on drinking days among treatment arm compared to placebo arm.
SECONDARY ENDPOINTS	
 • To detect 15-23% reductions in the urine positivity rate in the treatment arm compared to the placebo arm.
OTHER EVALUATIONS	Potential biomarkers for alcohol: EtG and PEth
SAFETY EVALUATIONS	Change in clinical safety labs from baseline to week 12 Incidence of adverse events
PLANNED INTERIM ANALYSES	No planned interim analyses. Serious adverse events will be monitored by the committee on an ongoing basis throughout the study.

STATISTICS Primary Analysis Plan	
We will use generalized estimating equations (GEE) to estimate treatment effects on repeated study outcomes. Primary analyses will be by intention-to-treat, without regard to adherence to treatment. In our prior trials, we had excellent retention and visit adherence. Nonetheless, in this high-risk population, missing data may be encountered.^{123, 124} We will conduct sensitivity analyses imputing all missing urine samples as positive, adjusting for baseline correlates of missingness, and using inverse probability of censoring weights.¹²⁵
 
Specific Aim 1: To determine the efficacy of targeted naltrexone versus placebo in reducing binge drinking among non-dependent MSM, as determined by number of binge drinking days in timeline follow-back (TLFB), by arm. GEE Poisson models with robust standard errors will be used to assess reductions on weekly drinking outcomes. Baseline TLFB results will be included in the analysis. Minimum detectable effects (MDEs): In calculating minimum detectable effects, we hypothesized on pharmacologic grounds that oral naltrexone will reach full efficacy against alcohol use almost immediately; accordingly we expect treatment-control differences to be approximately constant over the 12 weeks of the trial. Based on the prior trial (93% retention), we estimate that 90% of participants will be retained at 12 weeks. Using estimates based on data from Project ECHO⁹² for the within-subject correlation and over-dispersion of the outcomes, as well as the mean frequency among controls, we estimate that the proposed study will have 80% power in 2-sided tests with a type-I error rate of 5% to detect 27% reductions in numbers of binge drinking occasions, as well as 10% reductions in the average numbers of drinks on drinking days.
 
Specific Aim 2: To determine the efficacy of targeted naltrexone versus placebo in reducing alcohol consumption among non-dependent MSM, as determined by the proportion of ethyl glucuronide (EtG) positive urines, by arm. GEE logistic models with robust standard errors will be used to assess reductions frequency of positive urine tests, accounting for within-subject correlation. MDEs: Using the assumptions for loss to follow-up for Aim 1, as well as estimates based on biomarker data from Batki et al's study on Topiramate for alcohol use disorders¹²² for the within-subject correlation and control group urine positivity rate, we estimate that the study will have 80% power in 2-sided tests with a type-I error rate of 5% to detect 15-23% reductions in the urine positivity rate in the treatment arm.
 
Specific Aim 3: To determine the efficacy of targeted naltrexone versus placebo in reducing alcohol-associated sexual risk behaviors, we will use GEE Poisson models with robust standard errors for the four monthly ACASI assessments on numbers of male anal sex partners, HIV-serodiscordant unprotected anal sex partners, unprotected anal sex partners while intoxicated with alcohol, and unprotected anal sex events with serodiscordant partners, including the baseline value. In the event that these outcomes are severely over-dispersed, we will analyze indicators for any self-report of each behavior, using GEE logistic models. MDEs: Based on estimates of within-subject correlation and control prevalence from our Project Echo trial, we estimate that the study will have 80% power to detect 31% reductions in numbers of male anal sex partners, 57% reductions in SDUA partners, 46% reductions in UA partners while intoxicated with alcohol, and 56% reductions in UA events with serodiscordant partners. In

---	--

	analyses using GEE logistic models, we will have 80% power to detect reductions of 14%, 38%, 39%, and 30% in any report of these four sexual risk behaviors, respectively.
Rationale for Number of Subjects	Given our estimate that there are 48,070 binge-drinking MSM in San Francisco ^{19, 20} and our prior trial enrollment rates, we are confident that we will be able to recruit 120 eligible non-dependent, binge-drinking MSM for the proposed trial.

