5.3 Safety Evaluations

Change in clinical laboratory findings, specifically the liver enzymes such as BUN or Creatinine.
Incidence of adverse events

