9.1.6 Safety Lab Assessment

Safety lab assessments will take place at screening, months 1, 2, and 3 visits. Blood specimens will be collected for monthly safety lab assessments via venipuncture by clinicians or research associates with certified phlebotomy training. Medications taken 30 days prior to enrollment and while enrolled in the study will be documented on a concomitant medications form.

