10.6 Early Withdrawal Visit

Record any Adverse Experiences and/or Review subject diary for adverse experiences and exclusionary medication use.

Record changes to concomitant medications.

Perform complete physical examination.

Perform and record vital signs.

Collect blood for clinical laboratory tests: Chemistry, Hematology, Urinalysis, Pregnancy (urine or serum).

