11 ADVERSE EXPERIENCE REPORTING AND DOCUMENTATION

11.1 Adverse Events

An adverse event (AE) is any untoward medical occurrence in a clinical investigation of a patient administered a pharmaceutical product and that does not necessarily have a causal relationship with the treatment. An AE is therefore any unfavorable and unintended sign (including an abnormal laboratory finding), symptom or disease temporally associated with the administration of an investigational product, whether or not related to that investigational product. An unexpected AE is one of a type not identified in nature, severity, or frequency in the current Investigator's Brochure or of greater severity or frequency than expected based on the information in the Investigator's Brochure.

The Investigator will probe, via discussion with the subject, for the occurrence of AEs during each subject visit and record the information in the site's source documents. Adverse events will be recorded in the patient CRF. Adverse events will be described by duration (start and stop dates and times), severity, outcome, treatment and relation to study drug, or if unrelated, the cause.

AE Severity

The National Cancer Institute's Common Terminology Criteria for Adverse Events (CTCAE) Version 3.0 should be used to assess and grade AE severity, including laboratory abnormalities judged to be clinically significant. The modified criteria can be found in the study manual. If the experience is not covered in the modified criteria, the guidelines shown in Table 1 below should be used to grade severity. It should be pointed out that the term "severe" is a measure of intensity and that a severe AE is not necessarily serious.

Table 1. AE Severity Grading

Severity (Toxicity Grade)	Description
Mild (1)	Transient or mild discomfort; no limitation in activity; no medical intervention or therapy required. The subject may be aware of the sign or symptom but tolerates it reasonably well.
Moderate (2)	Mild to moderate limitation in activity, no or minimal medical intervention/therapy required.
Severe (3)	Marked limitation in activity, medical intervention/therapy required, hospitalizations possible.
Life-threatening (4)	The subject is at risk of death due to the adverse experience as it occurred. This does not refer to an experience that hypothetically might have caused death if it were more severe.

AE Relationship to Study Drug

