12 DISCONTINUATION AND REPLACEMENT OF SUBJECTS

12.1 Early Discontinuation of Study Drug

A subject may be discontinued from study treatment at any time if the subject or the investigator feels that it is not in the subject's best interest to continue. The following is a list of possible reasons for study treatment discontinuation:

Subject withdrawal of consent (or assent)

Subject is not compliant with study procedures

Adverse event that in the opinion of the investigator would be in the best interest of the subject to discontinue study treatment

Protocol violation requiring discontinuation of study treatment

Lost to follow-up

PI or clinician request for early termination of study

Positive pregnancy test (females)

If a subject is withdrawn from treatment due to an adverse event, the subject will be followed and treated by the Investigator until the abnormal parameter or symptom has resolved or stabilized.

All subjects who discontinue study treatment should come in for an early discontinuation visit as soon as possible and then should be encouraged to complete all remaining scheduled visits and procedures.

All subjects are free to withdraw from participation at any time, for any reason, specified or unspecified, and without prejudice.

Reasonable attempts will be made by the investigator to provide a reason for subject withdrawals. The reason for the subject's withdrawal from the study will be specified in the subject's source documents. Refer to Section 10 for early termination procedures.

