12.2 Withdrawal of Subjects from the Study

A subject may be withdrawn from the study at any time if the subject or the investigator feels that it is not in the subject's best interest to continue.

All subjects are free to withdraw from participation at any time, for any reason, specified or unspecified, and without prejudice.

Reasonable attempts will be made by the investigator to provide a reason for subject withdrawals. The reason for the subject's withdrawal from the study will be specified in the subject's source documents. As noted above, subjects who discontinue study treatment early (i.e., they withdraw prior to Week 8 Visit) should have an early discontinuation visit. Refer to Section 10 for early

termination procedures. Subjects who withdraw after Week 8 Visit but prior to Week 12 Visit should be encouraged to come in for a final visit (and the procedures to be followed would include those for their next scheduled visit).

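### The one dated laboratory safety evaluation is change from baseline to Week 12, and no analysis is stated for the Month 1, Month 2 and early-withdrawal panels

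*Combined protocol and SAP*

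**What the plan says.** The synopsis lists two safety evaluations: "Change in clinical safety labs from baseline to week 12" and "Incidence of adverse events". Section 5.3 repeats the laboratory item without a time point: "Change in clinical laboratory findings, specifically the liver enzymes such as BUN or Creatinine". BUN and creatinine are not liver enzymes, so that sentence does not settle which analytes are meant. AST and ALT are in the chemistry profile (Section 9.3.2).

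More panels are drawn than the synopsis line uses. Section 9.1.6 states: "Safety lab assessments will take place at screening, months 1, 2, and 3 visits". Section 10.5 repeats chemistry and hematology at each monthly visit, and Section 10.6 includes both at early withdrawal. Weekly visits are numbered 1-3, 5-7 and 9-11 (Section 10.4), so the Month 3 visit is the Week 12 visit.

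On analysis, Section 15.1 defines the Safety Population as eligible randomized participants who took at least one dose. Section 15.4 says that safety data are summarized by treatment group, and that adverse events are tabulated by arm with number of patients, rate, severity and relationship to drug. Section 15 defers detail to a SAP still to be written. No section gives a laboratory summary measure, a method for the Month 1, Month 2 or early-withdrawal values, or a rule for participants without a Week 12 panel.

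**The concern.** Laboratory safety questions usually turn on a few individual values at whatever visit they occur. A contrast between the screening panel and the Week 12 panel shows only where each man ended. A rise at Month 1 or Month 2 that has returned to normal contributes nothing, and a man without a Week 12 panel contributes nothing even if he had earlier post-baseline panels.

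Section 2.1 notes that naltrexone can injure liver cells at excessive doses, and Section 6.3 admits men with AST or ALT anywhere below 3 times the upper limit of normal. Starting values will therefore vary, and movement from each man's own baseline is what a reader will want to see. At stake is whether the report can show by arm, over all panels drawn and all men dosed, how many had a notable rise. As the plan is written, that would rest on the adverse-event tables.

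**Working it through.** The plan states no figure for this point, so there is none to reproduce. The following are counts from its own inputs.

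**Inputs**
- 120 participants, 60 per arm (Sections 8.1 and 15.6).
- Three scheduled post-baseline panels each, at Months 1, 2 and 3 (Section 9.1.6).
- Retention at 12 weeks of 90% planned, with 93% in the prior trial (Section 15.3).

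**Panels outside a literal Week 12 contrast**
- Scheduled post-baseline panels: 120 × 3 = 360.
- Scheduled at Week 12: 120 × 1 = 120.
- Scheduled at Months 1 and 2: 360 − 120 = 240, and 240/360 = 67%.
- Allowing for attrition, under the assumption that attendance falls evenly to 90%: 116 + 112 + 108 = 336 panels drawn, of which 116 + 112 = 228 are from Months 1 and 2, and 228/336 = 68%.

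Early-withdrawal panels come on top of these. Dividing the 108 panels expected at Week 12 by the 360 scheduled would give 70% unused, but that puts an attrition-reduced numerator over a full-attendance denominator. The like-for-like figure is 67% to 68%.

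**Participants with no Week 12 value**
- At 90%: 120 × 0.10 = 12, or 6 per arm.
- At 93%: 120 × 0.07 = 8.4, or about 4 per arm.

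**Does losing about 6 men per arm matter by itself?** Suppose each man has probability p of a notable abnormality, and loss is unrelated to it. The chance of seeing at least one such man in an arm of n is 1 − (1 − p)^n. The documents give no p, so a range is assumed.

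| Assumed p | n = 60 | n = 54 |
|---|---|---|
| 1% | 0.45 | 0.42 |
| 3% | 0.84 | 0.81 |
| 5% | 0.95 | 0.94 |
| 10% | 0.998 | 0.997 |

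Random loss of this size changes little. The loss matters if the men who leave are those with abnormal values, which the documents neither state nor exclude. The unused Month 1 and Month 2 panels are the larger part of the gap.

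**Which other routes could carry an early or unresolved rise?**
1. Adverse events. Section 11.1 counts as an adverse event any "unfavorable and unintended sign (including an abnormal laboratory finding), symptom or disease", but ties the grading of laboratory abnormalities to a judgment of clinical significance. Events are elicited by discussion (Section 11.1) and a checklist (Section 9.2.5). No numeric rule is applied to every panel.
2. Continued visits. After stopping drug, participants "should be encouraged to complete all remaining scheduled visits and procedures" (Section 12.1). This keeps many Week 12 panels but cannot guarantee them.
3. Late withdrawal. For men who withdraw after Week 8 and before Week 12, Section 12.2 says that "the procedures to be followed would include those for their next scheduled visit". If that is a Week 9, 10 or 11 visit, Section 10.4 lists no chemistry or hematology, so the last panel may be the Month 2 one.

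**The case against.** The strongest reply is that the plan already covers what matters clinically. An abnormal laboratory finding is an adverse event by definition, and adverse events are tabulated by arm with severity and relationship to drug. Men withdrawn from treatment for an adverse event are followed until it resolves or stabilizes (Section 12.1). The safety board receives laboratory data in total and by group (Section 14). The Safety Population has no completion requirement. The synopsis phrase may describe a period rather than two time points: Section 5.1 uses similar wording for the efficacy endpoints, and Section 5.3 gives no time point. A SAP is still to come.

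Much of this stands, and it rules out several stronger readings that a reader might infer:
- *Transient or treatment-stopping abnormalities are missed.* Not supported. Those judged clinically significant are graded and tabulated by arm, whatever the visit.
- *Everyone who stops drug before Week 12 drops out.* Not supported. Stopping drug is not leaving follow-up, and the plan asks these men to keep attending. The 90% is retention, not drug persistence.
- *The comparison is restricted to completers and biased toward no difference.* Not supported. No such restriction is written, and unused panels do not measure bias.
- *A mean change will hide individual rises.* The plan names no mean.
- *A liver signal is expected.* Section 2.1 ties hepatocellular injury to excessive doses, and cites a review that found no clinically significant liver disease from naltrexone.

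What the reply does not remove is the missing analysis. The adverse-event route depends on judgment, so a moderate rise not judged significant could go unsummarized. Board review is oversight rather than the reported analysis. If the phrase means a period, the plan still does not say how the values within it are to be summarized.

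**Conclusion.** The point holds as a gap in the stated laboratory analysis. Taken literally, the one dated evaluation leaves out up to 240 of 360 scheduled post-baseline panels (67%, or 68% under even attrition), and about 12 of 120 men at 90% retention (about 8 at 93%). Those men belong to the Safety Population if they took a dose. A transient rise, or one in a man who leaves follow-up, would then be reported only as an adverse event, and only if judged significant.

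This rests on three things: reading the synopsis phrase as a two-point contrast, which is natural but not forced; the plan's own retention figures; and the absence of any other laboratory method in the document, with the SAP still to be written. It does not invalidate the safety assessment. It is more than a request for detail, because a summary over all panels is clearly better than the stated contrast and the data for it will already exist.

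**What to change.** In the synopsis, Section 5.3 and Section 15.4, and then in the SAP before the final analysis:

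- Add a by-arm summary, in the Safety Population, of each participant's worst post-baseline value across the Month 1, 2 and 3 and early-withdrawal panels.
- Present it as a shift table from baseline, stating that the screening panel is the baseline.
- For AST and ALT, add the number of participants above stated multiples of the upper limit of normal. One could be 3 times, a figure Section 6.3 already uses for eligibility. These counts are for reporting only and carry no rule for managing participants.
- State how many participants in each arm have no post-baseline panel and how many have no Week 12 panel.
- Keep change from baseline to Week 12 as a supportive summary, and say which statistic it is.
- Correct Section 5.3 so that it names the analytes intended.

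The cost is one extra table. All the samples are already scheduled, and no visit, sample size or efficacy analysis changes.
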